8.7 Potential drug-induced liver injury (DILI)

Wherever possible, timely confirmation of initial liver-related laboratory abnormalities should occur prior to the reporting of a potential DILI event. All occurrences of potential DILI, meeting the defined criteria, must be reported as SAE.

Potential DILI is defined as:

1. ALT or AST elevation >3xULN

and

2. Total bilirubin >2xULN, without initial findings of cholestasis (elevated serum alkaline phosphatase)

and

3. No other immediately apparent possible causes of ALT/AST elevation and hyperbilirubinemia, including but not limited to viral hepatitis, pre-existing chronic or acute liver disease, or administration of other drug(s) known to be hepatotoxic.

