4.3 Inclusion criteria

All the following conditions must apply to the prospective patient at screening prior to receiving study treatment:

- Patient has histologically verified CRC adenocarcinoma (also comprising the mucinous adenocarcinoma and signet-ring cell carcinoma entities).
- Patient is ambulatory with Eastern Cooperative Oncology Group (ECOG) performance status 0 or 1 (*c.f.*, **Appendix 4**).
- Patient is at least 18 years of age.
- Patient has radiologically measurable metastatic disease.
- Patient has an intra-abdominal metastatic lesion that can be biopsied.
- Patient has not had previous systemic therapy for the metastatic disease.
- Patient is eligible for the Nordic FLOX regimen.
- Patient has the following laboratory values, as measured in serum/plasma within 14 days prior to study entry, indicative of adequate organ function:
 - Hemoglobin at least 10.0 g/dL.
 - Neutrophils at least $1.5 \times 10^9/L$ (without current use of colony-stimulating factors).
 - Platelets at least $100 \times 10^9/L$.
 - C-reactive protein less than 60 mg/L.
 - AST/ALT no higher than 2xULN when patient does not have metastatic disease in the liver or no higher than 5xULN when patient has metastatic disease in the liver.
 - Bilirubin no higher than 1.5xULN when patient does not have metastatic disease in the liver or no higher than 2xULN when patient has metastatic disease in the liver.
 - Albumin no lower than 30 g/L.
 - INR within normal level.
 - Creatinine no higher than 1.5xULN.
- Woman of childbearing potential (WOCBP)³ must have a negative serum or urine pregnancy test (minimum sensitivity 25 IU/L or equivalent units of HCG) within 24 hours prior to the start of study drug.
- WOCBP will use an adequate method⁴ to avoid pregnancy for a period of 26 weeks (which includes the required 30 days plus the time required for nivolumab to undergo five half-lives) after the last therapy dose, irrespective of study arm.
- Woman is not breastfeeding.

- Male who is sexually active with WOCBP must agree to follow instructions for method(s) of contraception⁴ for a period of 26 weeks (which includes the required time to ensure duration of sperm turnover plus the time required for the investigational drugs to undergo five half-lives) after the last therapy dose, irrespective of study arm.

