 - Other SmPC-listed contraindications for folinic acid and SmPC-listed contraindications for the other IMPs are covered by other exclusion criteria.
- Patient has undergone treatment with any IMP that may interfere with the study treatment within 4 weeks prior to first administration of study drug.
- Patient has known hypersensitivity to any of the study IMP components.
- Patient has ECOG performance status 2 or worse.
- Patient has serum/plasma CRP of 60 mg/L or higher.
- Patient does not meet the following requirements at baseline: adequate bone marrow function without current use of colony-stimulating factors (minimum values of neutrophils $1.5 \times 10^9/L$, platelets $100 \times 10^9/L$, hemoglobin 10 g/dL), adequate liver function (maximum values of AST/ALT 5xULN and bilirubin 2xULN; albumin value of 30 g/L or higher; INR within normal level), adequate renal function (maximum creatinine value of 1.5xULN).
- Patient has history of other prior malignancy, with the exception of curatively treated basal cell or squamous cell carcinoma of the skin, cervical cancer stage IB, stage I prostate cancer considered not necessary to treat, and another malignancy that was treated with curative intent more than 5 years ago and has not relapsed later.
- Patient has significant cardiac, pulmonary, or other medical illness that would limit activity of daily life (ADL) or survival.
- Patient is pregnant or breastfeeding.
- Patient has any other reason, in the opinion of Clinical Investigator, not to participate in the study.

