5.7.2.3 Treatment discontinuation criteria for IMP

For nivolumab, treatment will be permanently discontinued for the following reasons (in CTCAE grading):

- Any grade 4 drug-related AE.
- Any grade 2 drug-related uveitis, eye pain, or blurred vision that does not respond to topical therapy and does not improve to grade 1 severity within the re-treatment period or requires systemic treatment.
- Any grade 3 non-skin, drug-related AE lasting >7 days, with the following exceptions for laboratory abnormalities, drug-related uveitis, pneumonitis, bronchospasm, hypersensitivity reactions, infusion reactions, and endocrinopathies:
 - Grade 3 drug-related uveitis, pneumonitis, bronchospasm, hypersensitivity reaction, or infusion reaction of any duration (requires discontinuation).
 - Grade 3 drug-related endocrinopathies that are adequately controlled with only physiologic hormone replacement (do not require discontinuation).
 - Grade 3 drug-related laboratory abnormalities (do not require treatment discontinuation) except grade 3 drug-related thrombocytopenia >7 days or associated with bleeding (requires discontinuation).
- Any drug-related liver function test abnormality that meets the following criteria (requires discontinuation):
 - AST or ALT >5xULN.
 - Total bilirubin >3xULN.
- Any grade 4 drug-related AE or laboratory abnormality, except for one of the following events (does not require discontinuation):
 - Grade 4 neutropenia ≤7 days.
 - Grade 4 lymphopenia or leukopenia.
 - Isolated grade 4 amylase or lipase abnormalities that are not associated with symptoms or clinical manifestations of pancreatitis. Study Conduct Group (*c.f.*, [Paragraph 11.3](#)) should be consulted for grade 4 amylase or lipase abnormalities.
 - Isolated grade 4 electrolyte imbalances/abnormalities that are not associated with clinical sequelae and are corrected with supplementation/appropriate management within 72 hours of their onset.
 - Grade 4 drug-related endocrinopathy adverse events, such as adrenal insufficiency, ACTH deficiency, hyper- or hypothyroidism, or glucose intolerance, which resolve or are adequately controlled with physiologic hormone replacement (corticosteroids, thyroid hormones) or glucose-controlling agents, respectively, may not require discontinuation after discussion with and approval from Study Conduct Group.

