### **5.5. Harms**

The safety data will be recorded and reported according to severity, expectedness, and causality. Only CTCAE grade 3-5 will be recorded. CTCAE grade 2 events will be recorded only for immune-related hepatotoxicity (increased hepatic enzymes).

The following events will be individually recorded and reported according to prevailing national procedures:

Pregnancy (including pregnancy occurring in a female partner of a male study participant), overdose, and SUSARs. The events will be analyzed on incidence case basis. Each site investigator is responsible for assuring that there are procedures and expertise available to cope with emergencies during the study.

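### Liver harm may be inconsistently classified in patients with liver metastases who enter with raised liver tests, and no planned analysis refers those tests to baseline

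*Protocol*

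**What the plan says.** **Entry.** Protocol 4.3 admits patients with AST/ALT "no higher than 5xULN when patient has metastatic disease in the liver" and bilirubin "no higher than 2xULN when patient has metastatic disease in the liver". Without liver metastases the ceilings are 2xULN and 1.5xULN. Protocol 4.4 repeats only the higher pair: "maximum values of AST/ALT 5xULN and bilirubin 2xULN".

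**Potential DILI.** Protocol 8.7 makes every occurrence an SAE and joins three conditions by *and*:
- First criterion: "ALT or AST elevation >3xULN"
- Second criterion: "Total bilirubin >2xULN, without initial findings of cholestasis (elevated serum alkaline phosphatase"
- Third criterion: "No other immediately apparent possible causes of ALT/AST elevation and hyperbilirubinemia, including but not limited to viral hepatitis, pre-existing chronic or acute liver disease". Hepatotoxic co-medication is named there as well.

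**Stopping nivolumab.** Protocol 5.7.2.3 lists "Any drug-related liver function test abnormality that meets the following criteria (requires discontinuation", the criteria being AST or ALT above 5xULN, or total bilirubin above 3xULN.

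**Recording and analysis.** SAP 5.5 limits recording to CTCAE grades 3 to 5, with one exception: "CTCAE grade 2 events will be recorded only for immune-related hepatotoxicity (increased hepatic enzymes". SAP 5.2 summarises SAE counts and CTCAE grades by arm and compares arms by chi-square or Fisher's exact test. SAP 5.4 plans nothing further.

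**Data.** Protocol 7.4 schedules liver tests within 14 days before the first dose and within 3 days before each later dose, but allows that some assessments in that section may not reach the CRF.

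**The concern.** Hepatic events are a named class of immune-related harm (Protocol 5.4, 5.7.2.5), and the liver is a qualifying metastatic site (SAP 4.2). In a patient whose transaminases are already raised by tumour, a threshold counted from the ULN does not separate what the patient brought into the trial from what happened on treatment. Neither the DILI limits nor the stop limits refer to the patient's own baseline.

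Two features make the classification depend on judgement. The third DILI criterion excludes cases with another apparent cause and names pre-existing liver disease, without saying how liver metastases are to be treated. The grade 2 recording rule depends on an investigator calling the event immune-related in an open-label trial where only one arm receives nivolumab. At stake is how cleanly liver toxicity can be compared between arms. The efficacy analyses are not affected.

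**Working it through.** The plan states no figure on this point, so there is none to reproduce. The check sets its limits side by side.

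**1. Margin from the highest admissible entry value.** Formula: limit divided by entry ceiling. Below 1 means the limit can be exceeded at entry; exactly 1 means that any rise from the ceiling crosses it.

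| Group and test | Entry ceiling (xULN) | DILI limit | Ratio | Nivolumab stop limit | Ratio |
|---|---|---|---|---|---|
| Liver metastases, AST/ALT | 5 | >3 | 3/5 = 0.6 | >5 | 5/5 = 1.0 |
| Liver metastases, bilirubin | 2 | >2 | 2/2 = 1.0 | >3 | 3/2 = 1.5 |
| No liver metastases, AST/ALT | 2 | >3 | 3/2 = 1.5 | >5 | 5/2 = 2.5 |
| No liver metastases, bilirubin | 1.5 | >2 | 2/1.5 = 1.33 | >3 | 3/1.5 = 2.0 |

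Only the AST/ALT component of DILI, and only in patients with liver metastases, can be exceeded before treatment.

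**2. The full DILI definition at entry.** Eligibility requires bilirubin ≤2xULN; the second criterion requires >2xULN. Both cannot hold, so no eligible pair of AST/ALT and bilirubin values meets criteria 1 and 2 together.

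**3. The third criterion.** For a patient with liver metastases whose tests cross both limits on treatment, 8.7 allows two readings. If the metastases count as another cause, the case is not potential DILI; if they do not, it is an SAE. Protocol 8.9 leaves a similar choice, since an event may be called unrelated when concurrent disease is a reasonable cause. Two sites can therefore classify the same case differently.

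**4. Grade 2 recording by arm.** Under SAP 5.5 a grade 2 enzyme rise is recorded if it is judged immune-related. Control patients receive no nivolumab, so the same rise there is unlikely to be given that label.

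**5. Illustration of the AST/ALT margin.** My assumptions, not the plan's: a stable true level m (in xULN), lognormal within-patient variation with CV 10–30%, no drug effect, and 8 independent tests (the eight visits of one treatment sequence in the Study Flow Chart).

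s = √ln(1 + CV²); p = 1 − Φ(ln(5/m)/s); chance of at least one value >5xULN = 1 − (1 − p)^8.

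For m = 4 and CV 20%: s = 0.198, ln(5/4) = 0.223, p = 0.130, and 1 − 0.870^8 = 0.67.

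| Stable level | CV 10% | CV 20% | CV 30% |
|---|---|---|---|
| 3xULN | 0% | 4% | 28% |
| 4xULN | 10% | 67% | 87% |
| 4.5xULN | 72% | 94% | 97% |

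These are raw crossings of 5xULN, not stopping events, which also need a judgement that the abnormality is drug-related. The documents give no baseline AST/ALT distribution, so the table cannot be turned into a number of patients.

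**The case against.** The strongest reply is that the limits touch without contradicting each other: AST/ALT entry is ≤5 and the stop limit is >5; bilirubin entry is ≤2 and the DILI limit is >2. That stands. A reader might infer that some patients meet DILI on entry or have already breached the stop limit. Neither follows, because the bilirubin condition excludes the first and a pre-dose elevation cannot be drug-related.

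A reader might also infer that liver toxicity is judged only against the ULN. It is not. The AE definition (Protocol 8.1) covers worsening of an existing condition, dosing may resume at the patient's baseline value (5.7.2.2), and laboratory toxicities are followed until they resolve, return to baseline or are deemed irreversible (7.4). The hepatic algorithm of Appendix 5 lies in a separate document that was not available. These rules govern reporting and management; none supplies a baseline-referenced analysis.

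That liver harm *will* be misreported is likewise not shown. A case that fails the third criterion can still be an SAE through hospitalisation, threat to life or medical importance (8.1.2), or doubt about seriousness (8.2). Laboratory abnormalities that interrupt or stop treatment, or need correction, are captured (8.4). Protocol 8.10.1 has all AE recorded in the CRF; SAP 5.5 is the narrower text. Nor does 8.7 make liver metastases an automatic other cause: it is silent, so no direction of error can be claimed.

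Entry criteria are the same in both randomised arms, so raised baselines should be broadly balanced and mainly add noise. That does not answer the grade 2 rule, which works through attribution and can differ by arm.

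Finally, the illustration is weak evidence. It assumes independent tests, and the first of the eight precedes any drug; with seven tests the 67% becomes 1 − 0.870^7 = 62%. It shows only that the margin is narrow at high baselines.

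**Conclusion.** The point holds in a limited form. In patients with liver metastases, the AST/ALT component of potential DILI can be met before treatment, and the AST/ALT entry ceiling coincides with the nivolumab stop limit. The third DILI criterion leaves the role of liver metastases open, and SAP 5.5 ties grade 2 recording to an immune-related label. Liver harm may therefore be inconsistently classified in patients with raised baselines, and grade 2 enzyme rises may not be recorded equally in both arms.

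The size is unknown. The 10–87% at a stable 4xULN is conditional on that level and on the assumed variation; it is not a share of the 100 patients. This is a cheap improvement to the safety analysis, not a flaw in the primary comparison.

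**What to change.** **Data.** Enter the baseline and pre-dose ALT, AST and bilirubin values in the CRF for both arms.

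**SAP 5.2 and 5.5.** For each test, add shift tables from baseline CTCAE grade to worst on-treatment grade, and the ratio of worst on-treatment value to baseline. Present them by arm and by liver involvement, regardless of attribution. Count as treatment-emergent only worsening from the baseline grade. List potential DILI twice, with and without the third criterion. Amend SAP 5.4 accordingly.

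**Protocol.** The sponsor's clinicians should reconcile the limits in 4.3, 4.4, 5.7.2.3 and 8.7, and state how liver metastases and raised baselines are handled. No threshold or clinical rule is proposed here.

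**Cost.** SAP wording, a few tables and one listing. The tests are already scheduled before every dose. The downside is data entry: 3 tests × 8 visits = 24 values per patient in a full eight-cycle sequence, plus baseline. Protocol 10.4.1 allows changes to the plan until database lock, but values not entered during the trial would have to be retrieved from the medical records, so the CRF change should come first.

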8.8 Other safety considerations

Any significant worsening noted during interim or final physical examinations, radiology examination, or any other potential safety assessment required or not required by protocol should also be recorded as a non-serious AE or SAE, as appropriate, and reported accordingly.

8.9 AE (adverse events) recording

If the patient has experienced an AE, Clinical Investigator will record the following information in the CRF:

- The nature of the AE will be described in precise standard medical terminology (*i.e.*, not necessarily the exact words used by the patient).
- The duration of the event will be described in terms of event onset date and event ended date.
- The intensity of the AE will be defined according to CTCAE v4.0.
- The causal relationship of the event to the IMP will be assessed as one of the following:

Unrelated: There is no temporal relationship to IMP administration (too early or late, or IMP not administered), or there is a reasonable causal relationship between non-investigational product, concurrent disease, or circumstance and the AE.

Unlikely: There is a temporal relationship to IMP administration, but there is not a reasonable causal relationship between the IMP and AE.

Possible: There is reasonable causal relationship between the IMP and AE. Dechallenge information is lacking or unclear.

Probable: There is a reasonable causal relationship between the IMP and AE. The event responds to dechallenge. Rechallenge is not required.

Definite: There is a reasonable causal relationship between the IMP and AE.

- Action taken.
- The outcome of the AE – whether the event is resolved or still ongoing.

It is important to distinguish between serious and severe AE. Severity is a measure of intensity whereas seriousness is defined by the criteria in Paragraph 8.1.2. An AE of severe intensity needs not necessarily be considered serious. For example, nausea that persists for several hours may be considered severe nausea, but is not an SAE. On the other hand, a stroke that results in only a limited degree of disability may be considered a mild stroke, but would be an SAE.

8.10 Reporting procedure

8.10.1 AE (adverse events) and SAE (serious adverse events)

All AE and SAE will be recorded in the patient's CRF.

SAE must be reported by Clinical Investigator to Sponsor by email and telephone to Principal Investigator, within 24 hours after the site has gained knowledge of the SAE (*c.f.*, Paragraph 8.2). Every SAE must be documented by Clinical Investigator on the SAE pages (to be found in Investigator Site File). The SAE report form must be completed, signed, and sent to Sponsor. The initial report shall promptly be followed by detailed, written reports if necessary. The initial and follow-up reports shall identify the trial subjects by unique code numbers assigned to the latter.

Sponsor will keep detailed records of all SAE reported by the investigators and performs an evaluation with respect to seriousness, causality, and expectedness.

8.10.2 SUSAR (suspected unexpected serious adverse reactions)

SUSAR will be reported to the Competent Authority and Ethics Committee according to national regulation. The following timelines should be followed (pertaining to both study arms):

Sponsor will ensure that all relevant information about SUSAR that are fatal or life-threatening is recorded and reported as soon as possible to the Competent Authority and Ethics Committee, in any case no later than seven (7) days after knowledge by Sponsor of such a case, and that relevant follow-up information is subsequently communicated within an additional eight (8) days.

All other SUSAR will be reported to the Competent Authority concerned and Ethics Committee as soon as possible but within a maximum of fifteen (15) days of first knowledge by the sponsor.

SUSAR will be reported using the CIOMS form.

8.10.3 Annual safety report

Once a year throughout the clinical study, Sponsor will provide the Competent Authority with an annual safety report. A final safety report will also be provided at study conclusion. The format will comply with national requirements.

8.10.4 Clinical study report

The AE and SAE occurring during the study will be discussed in the safety evaluation part of the clinical study report.

8.11 Procedures in case of emergency

Clinical Investigator is responsible for assuring that there are procedures and expertise available to cope with emergencies during the study.

9 DATA MANAGEMENT AND MONITORING

9.1 Database management

All data will be collected and collated in the the web-based data management system, termed Viedoc, which includes web-based CRF with an ancillary eDatabase, randomization procedures, and validation of data, and which meets regulatory requirements for clinical therapy trials. This service will be purchased from the South-Eastern Norway Regional Health Authority's Clinical Trial Unit, Oslo University Hospital.

9.2 CRF (case report forms)

The designated investigator staff will enter the data required by the protocol into the electronic CRF. Clinical Investigator is responsible for assuring that data entered into the CRF is accurate and complete. The signature of Clinical Investigator will attest the accuracy of the data on each CRF. If any assessments are omitted, the reason for such omissions will be noted on the CRF. Corrections, with the reason, will also be recorded.

After database lock, Principal Investigator will receive copies of the subject data for archiving at the investigational site.

9.3 Source data

The medical records for each patient will contain information which is important for the patient's safety and continued care, and to fulfill the requirement that critical study data will be verifiable.

To achieve this, the medical records of each patient should clearly describe at least:

- That the patient is participating in the study, e.g., by including the enrolment number and the study code or other study identification.
- Date when ICF was obtained from the patient and statement that patient received a copy of the signed and dated ICF.
- Results of all assessments confirming a patient's eligibility for the study.
- Diseases (past and current, both the disease studied and others, as relevant).
- Treatments withdrawn/withheld due to participation in the study.
- Results of assessments performed during the study.
- ECOG performance status assessments conducted as part of the study.
- Treatments given, changes in treatments during the study, and the time points for the changes.
- Visits to the clinic and telephone contacts during the study, including those for study purposes only.
- Non-serious AE and SAE (if any), including causality assessments.
- Date of and reason for discontinuation from study treatment.
- Date of and reason for withdrawal from study.
- Date of death and cause of death, if available.
- Additional information according to local regulations and practice.

9.4 External Data and Safety Monitoring Committee

The External Data and Safety Monitoring Committee (EDSMC) will oversee the trial during its entire course. EDSMC will consist of two board-certified specialists in oncology and one medical statistician, all of whom are independent from Sponsor and with no competing interests. EDSMC will review treatment response and safety data after each twentieth consecutive study patient has been accrued, or more frequently should there be a medical indication for a review identified by an EDSMC member or an investigator.

EDSMC will have particular focus on data indicating unexpectedly good treatment responses (e.g., a 'miraculous' response leading to potential curation of patient), possible responses detrimental for experimental arm patients, and unexpected toxicities from the sequential therapy (i.e., SUSAR or SAE and SUSAR-like toxicities not foreseen and therefore not described in the study protocol). In case of such data, EDSMC will immediately confer with Study Conduct Group (c.f., [Paragraph 11.3](#)) about the immediate further conduct and management of the study.

EDSMC actions related to interim analyses are detailed in [Paragraph 10.4.2](#). If the number of PFS events in the experimental arm at any review is twice the number of PFS events in the control arm, EDSMC may consider early study termination.

The EDSMC members will be:

- [name], MD PhD, Oslo University Hospital (expertise in clinical immune therapy studies)
- [name], MD PhD, Oslo University Hospital (expertise in clinical CRC studies)
- [name], PhD, Oslo University Hospital (expertise in statistical methods in medical research)

